#### H3N2 M2SR Vaccine

Intranasal LAIV vaccines have induced nasal edema, nasal dryness, nasal pain/irritation, nasal congestion, rhinorrhea, decreased appetite, irritability, decreased activity, fatigue, malaise, sore throat (pharyngitis), difficulty swallowing, headache, arthralgia, myalgia, fever, feverishness (chills, shivering, sweating), cough, abdominal pain, nausea, vomiting, diarrhea, ear infections, conjunctivitis, itchy eyes, flushing, sinusitis, sneezing, nasal bleeding, shortness of breath, allergy, and wheezing/rhonchi in young children. Rarely, nosebleeds can occur after intranasal

vaccinations. Because H3N2 M2SR vaccine is a live attenuated vaccine given intranasally similar to other LAIV, we will specifically study these symptoms as solicited AEs.

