- Approximately 16 mL of PBMCs will be collected for IFN- $\gamma$  ELISPOT and CFSE dilution/ICS assays.
- A urine pregnancy test will be performed on all female adolescent subjects of childbearing potential and must be negative to ensure eligibility.
- Subjects will be enrolled in AdvantageEDCSM and assigned randomly to a treatment arm prior to the first study vaccination.
- Pre-administration reactogenicity assessments will be performed prior to the first study vaccination to establish baseline. Subjects will then receive a single dose of study product or placebo intranasally. Subjects will be observed in the clinic for at least 30 minutes after the first study vaccination. Post-administration reactogenicity assessments will be completed, and any AE/SAEs will be recorded on the appropriate data collection form prior to discharge from the clinic.
- Parent(s)/legal guardian(s) will be provided with a memory aid and other study-related materials to record daily oral temperature, solicited systemic reactions, any unsolicited AEs, and concomitant medications. Parent(s)/legal guardian(s) will be encouraged to take child's oral temperature around the same time each day. Subjects must not eat or drink anything hot or cold, or smoke within 10 minutes prior to taking oral temperature. Parent(s)/legal guardian(s) will be instructed on how to use their memory aid and how to measure and record AEs prior to discharge from the clinic. Parent(s)/legal guardian(s) will be instructed to notify the study center if they develop any severe reactions after the first study vaccination. If the site principal investigator or appropriate sub-investigator deems the reaction severe enough, further instructions will be given to the parent(s)/legal/guardian(s) on the proper course of action, including a return to the clinic for immediate evaluation if appropriate.

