- At the screening visit a physical examination will be performed on all subjects to include the following organs and organ systems: including skin, head and neck including upper respiratory tract (nares and nasopharynx), lungs, heart, liver, spleen, extremities, lymph nodes, and nervous system, by a study clinician licensed to make medical diagnoses and listed on the Form FDA 1572 as the site principal investigator or sub-investigator. At Visit 01, 02 and Early Termination or Unscheduled Visits if they occur within 8 days of vaccination after the first study vaccination, a limited physical examination to include the nares (including edema), throat, and lungs will be performed and a targeted physical examination may be performed on the other body systems, if indicated based on the subject's interim medical history, by a study clinician licensed to make medical diagnoses and listed on the Form FDA 1572 as the site principal investigator or sub-investigator. At all other follow-up visits, a targeted physical examination may be performed, if indicated based on review of interim medical history, by a study clinician licensed to make medical diagnoses and listed on the Form FDA 1572 as the site principal investigator or sub-investigator.

Oral temperature will be collected prior to each study vaccination. Subjects must not eat or drink anything hot or cold, or smoke within 10 minutes prior to taking oral temperature.

Reactogenicity assessments will include an assessment of solicited AEs occurring from the time of experimental (first) study vaccination through Day 8 after vaccination. For upper respiratory symptoms, this includes an assessment of runny nose, stuffy nose/ congestion, sneezing, nasal pain/irritation/nasal dryness, nasal bleeding/epistaxis, sinus pressure/pain, sore throat/sore/scratchy, itchy or painful throat, cough, trouble breathing/shortness of breath. For general systemic symptoms, this includes an assessment of reactions including fever, feverishness (chills/shivering/sweating), fatigue (tiredness), malaise, myalgia (body aches/muscular pain), arthralgia (joint pain), headache, flushing, decreased activity, decreased appetite, abdominal pain, nausea, vomiting, diarrhea, eye pruritus, eye redness (conjunctivitis), and allergy. For respiratory tract symptoms, this will include an assessment of nares' erythema and induration.

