#### **Local (Upper Respiratory) Reactogenicity Grading**

Local (Nasal) Reaction	Mild (Grade 1)	Moderate (Grade 2)	Severe (Grade 3)
Runny Nose	Noticeable but does not interfere with daily activity	Moderate discomfort/interferes with daily activity	Significant discomfort/prevents daily activity or seeks medical encounter

Local (Nasal) Reaction	Mild (Grade 1)	Moderate (Grade 2)	Severe (Grade 3)
Stuffy Nose/Congestion	Noticeable but does not interfere with daily activity	Moderate discomfort/interferes with breathing from nose	not being able to breath from nose, or prevents daily activity or seeks medical encounter
Sneezing	Noticeable but does not interfere with daily activity	Moderate discomfort. Interferes with daily activity	Significant discomfort/prevents daily activity
Nasal Pain/Irritation	Noticeable but does not interfere with daily activity	Moderate discomfort/interferes with daily activity	Significant discomfort/prevents daily activity or seeks medical encounter
Nasal Bleeding/Epistaxis	Total duration of all episodes in a 24 hour period <30 minutes	Total duration of all episodes in a 24 hour period $\geq$ 30 minutes	Any bleeding that required visit for medical encounter
Sinus Pressure/Pain	Noticeable but does not interfere with daily activity	Moderate discomfort. Interferes with daily activity	Significant discomfort/prevents daily activity
Sore Throat/Sore/Scratchy/ Itchy or Painful Throat	Noticeable but does not interfere with eating and/or drinking	Moderate discomfort. Interferes with eating and/or drinking	Significant discomfort/prevents eating and/or drinking or seeks medical encounter
Cough	Noticeable but does not interfere with daily activity or sleeping	Moderate discomfort/interferes with daily activity or sleeping	Significant discomfort/prevents daily activity or seeks medical encounter
Trouble breathing/Shortness of Breath	Noticeable but does not interfere with daily activity or not	Moderate discomfort/interferes with daily activity or	Significant discomfort/prevents daily activity or seeks

Local (Nasal) Reaction	Mild (Grade 1)	Moderate (Grade 2)	Severe (Grade 3)

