**Quantitative Systemic Reactogenicity Grading**

Systemic (Quantitative)	Mild (Grade 1)	Moderate (Grade 2)	Severe (Grade 3)
Fever* - oral †	38.0°C – 38.4°C 100.4°F – 101.1°F	38.5°C – 38.9°C 101.2°F – 102.0°F	>38.9°C >102.0°F

# Oral temperature assessed on Day 1 prior to the first study vaccination will be considered as baseline.

\* A fever can be considered not related to the study product if an alternative etiology can be documented.

† Subjects must not eat or drink anything hot or cold, or smoke within 10 minutes prior to taking oral temperature.

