#### **9.5. Halting Rules**

Further enrollment and study vaccinations will be halted for SMC review/recommendation if any of the following are reported following experimental (first) vaccination:

- Any subject experiences laryngospasm, bronchospasm, or anaphylaxis within 1 day after administration of study product that is considered related to study product.
- Two or more subjects experience the same grade 3 Adverse Event of any kind after administration of study product through day 8 that is considered related to study product
- Two or more subjects experience generalized urticaria (defined as occurring at more than two body parts) within 3 days after administration of study product that is considered related to study product.

- Any subject experiences a study vaccine-related SAE from the time of the first study vaccination through the subject's last study visit.

Grading scales for solicited upper respiratory and systemic (subjective and quantitative) reactions are included in [Section 9.2.2](#).

If any of the halting rules are met following any subject receipt of the first study vaccination, then this trial will not continue with the remaining enrollments or study vaccinations without a review by and recommendation from the SMC to proceed.

DMID retains the authority to suspend additional enrollment and study interventions/ administration of study product during the entire trial, as applicable.

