#### **11.4.2. Primary Safety Data**

Summaries and analysis of safety data will be presented for the Safety Analysis Population.

Solicited AEs will be summarized by severity for each day after the first study vaccination (Days 1-8 post vaccination) and as the maximum severity over all 8 days. Additionally, solicited AEs will be analyzed by taking the most severe response over the follow-up period, dichotomizing into a binary variable (none versus mild, moderate, or severe) and using standard techniques, such as exact confidence intervals, to summarize the number and percentage of subjects reporting each symptom, any upper respiratory symptom and any systemic symptom by treatment arm.

Unsolicited AEs will be coded by Medical Dictionary for Regulatory Activities (MedDRA®) for preferred term and system organ class (SOC). The number of SAEs, AESIs, and NOCMCs is expected to be small in this trial and will be reported by detailed listing showing the event description, MedDRA preferred term and SOC, relevant dates (study vaccinations and AEs), severity, relatedness, and outcome for each event. If more than 5% of subjects report SAEs, and AESIs, and NOCMCs then the number and percentage of subjects reporting each type of event will be reported by treatment arm and compared using Fisher's Exact test. Unsolicited AEs will be summarized as number and percentage of subjects reporting at least one event in each MedDRA preferred term and SOC, cross tabulated by severity and relationship to study product. Additionally, the proportion of subjects and exact 95% confidence intervals of AEs in aggregate and by MedDRA categories will be computed.

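### Measured fever is solicited, recorded daily and graded, but it is the one event named in SAP 9.3.1 with no row in the solicited-event shells (SAP Tables 40-44)

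*Protocol*

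**What the plan says.** Protocol 2.3.1 includes fever in its list of reactions to intranasal live vaccines and says of M2SR, as a live attenuated vaccine "given intranasally similar to other LAIV, we will specifically study these symptoms as solicited AEs". Fever is an event in its own right throughout the operative text.

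- **Solicited.** Protocol 8.1 puts it first: "For general systemic symptoms, this includes an assessment of reactions including fever, feverishness (chills/shivering/sweating), fatigue (tiredness), malaise". SAP 9.3.1 gives the same systemic list, again with fever and feverishness as separate entries.
- **Collected.** At Visit 01 families receive a memory aid "to record daily oral temperature, solicited systemic reactions, any unsolicited AEs, and concomitant medications" (Protocol 7.3.1).
- **Graded.** Protocol 9.2.2 has a separate scale for it, headed "Quantitative Systemic Reactogenicity Grading", with oral temperature cut-offs. SAP Table 7 repeats the scale.
- **To be summarised.** Protocol 11.4.2 plans exact intervals and similar methods "to summarize the number and percentage of subjects reporting each symptom, any upper respiratory symptom and any systemic symptom by treatment arm". SAP 9.3.1 asks for a proportion with a 95% interval for each solicited event (Table 40), the between-arm difference (Table 41), maximum severity (Table 42) and counts by day (Tables 43 and 44).

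In the shells for Tables 40 to 43, the systemic block goes from the any-systemic line directly to feverishness. There is no fever row. Table 44 is not drawn and is said only to have similar formatting to Table 43.

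**The concern.** The SAP text and the SAP shells disagree, and tables are programmed from shells. Frequency of solicited upper respiratory and systemic reactogenicity is the first primary outcome (Protocol 3.2.1). For a live intranasal vaccine in children, fever is one of the reactions a reader will look for first, and it is the only solicited reaction in SAP Table 7 graded by measurement rather than by report.

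At stake is the by-arm summary of one primary-outcome component: how many subjects in each arm had fever, at what grade, on which days, with what interval, and the difference between arms. Collection of the data is not in question.

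**Working it through.** The plan gives no figure to reproduce. The check matches two lists item by item.

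**Events named in SAP 9.3.1**

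- Systemic: fever, feverishness, fatigue, malaise, myalgia, arthralgia, headache, flushing, decreased activity, decreased appetite, abdominal pain, nausea, vomiting, diarrhea, eye pruritus, eye redness, allergy = 17.
- Local: runny nose, stuffy nose, sneezing, nasal pain, nasal bleeding, sinus pressure, sore throat, cough, trouble breathing = 9.
- Wheezing on or before Day 8 = 1.
- Total: 17 + 9 + 1 = 27.

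**Individual-symptom rows in the shells**

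| Shell | Systemic rows | Local rows | Total | Named event without a row |
|---|---|---|---|---|
| Table 40 | 16 + wheezing = 17 | 9 | 26 | fever |
| Table 41 | 16 + wheezing = 17 | 9 | 26 | fever |
| Table 42 | 16 + wheezing = 17 | 9 | 26 | fever |
| Table 43 | 16 + wheezing = 17 | 9 | 26 | fever |
| Table 44 | not drawn; follows Table 43 | | | fever, by inference |

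The shortfall is 27 − 26 = 1. Four drawn shells agree, so a broken table in the source file is not the explanation. The 16 systemic rows other than wheezing are the 16 subjective items of SAP Table 7. Probably those were carried over and the single quantitative item was left behind.

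**Can the feverishness row stand in?** No. Feverishness (chills, shivering, sweating) is graded by interference with daily activity. Fever is graded by oral temperature: 38.0–38.4 °C, 38.5–38.9 °C and above 38.9 °C. A subject can have either without the other.

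**Do other outputs supply the missing summary?**

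- Table 38 gives systemic events by arm and grade, pooled over all systemic symptoms.
- Figure 50 gives maximum severity by day, also pooled.
- Listing 11 shows graded temperatures subject by subject, with no rate or interval.
- Table 39 shows only events in at least 5% of subjects in an arm. With 25 per arm, one subject is 1/25 = 4% and is dropped; two are 2/25 = 8% and are shown. Its shell has no grade or interval, and the SAP does not say clearly that solicited events enter it.

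None gives fever by arm with its grade and interval.

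**The case against.** The best defence is that the SAP preface calls the shells sample tables, that the text of 9.3.1 names fever and requires its summary, and that a competent programmer would add the row. With about 25 subjects per arm, a reader could also count fevers from Listing 11. It is true that the text is right and the data will be there. But these shells write out every other symptom and even give wheezing its own not-applicable cells by day. They carry no note allowing extra rows, unlike Table 17. Nothing says that the text prevails where the two conflict. A listing does not supply the denominator, interval and between-arm difference that the text promises.

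It is also fair to say that fever's place in the totals is already settled. SAP 9.3.1 lists fever among the systemic events and then asks for an any-systemic summary. That objection stands: a table note would confirm the rule, not create it. Nothing in the documents suggests that fever would be left out of the interim Table 38.

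A reader might infer that the missing row weakens safety monitoring, because halting is triggered when "Two or more subjects experience the same grade 3 Adverse Event of any kind after administration of study product through day 8" and the event is considered related (Protocol 9.5). The documents do not support this. Halting acts on events as reported, through the Medical Monitor and the Safety Monitoring Committee, and SAP Tables 40-44 are not among those marked for the interim analysis. The gap affects the final report.

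**Conclusion.** The point holds as a conflict between SAP text and SAP shells: 1 of the 27 named solicited events has no row, across five tables. As drawn, the solicited-event tables would give no fever rate, grade or interval by arm for a primary safety outcome. It is minor in effort and in kind, since collection, grading and listing of temperatures are all in place, but the omitted row matters to anyone reading the safety results.

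Two assumptions carry this: that the shells are programmed as drawn, and that Table 44 takes its rows from Table 43.

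A reader might go further and count how many reactions named in Protocol 2.3.1 never reach the solicited tables. The documents do not support a finding on that basis. Section 2.3.1 is background risk text, and the operative lists in Protocol 8.1 and SAP 9.3.1 agree on which upper respiratory and systemic symptoms are solicited. Several of the 2.3.1 terms are handled elsewhere: nasal edema through the graded nares induration assessment, and ear infection through otitis media as an event of special interest. Irritability and difficulty swallowing have no named item, but the sore-throat item is graded on eating and drinking (Grade 1 reads "Noticeable but does not interfere with eating and/or drinking"), and either could be reported as an unsolicited event through Day 21. The memory aid is not in the documents, so what families were asked cannot be checked. At most, the 2.3.1 sentence is broader than the specified solicited list, which is an editorial remark and alters no result.

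**What to change.** 1. Add a measured-fever row, graded by the oral temperature scale in SAP Table 7, to the systemic block of Tables 40, 41, 42 and 43, and so to Table 44. Keep it separate from feverishness.
2. Add a table note confirming that fever counts in the any-systemic and any-symptom lines, in keeping with SAP 9.3.1.
3. Optionally, narrow the 2.3.1 sentence so that it refers to the solicited list in Protocol 8.1.

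The cost is one row in each of five tables and a note. Daily oral temperature is already collected, so no new data, visit or memory-aid change is needed.

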### Placebo

The placebo is physiological saline or 0.9% sodium chloride for injection. Side effects do not typically occur from administration of this solution to the nasal passages. If the subject's nasal passages are extremely dry or irritated it is possible they may experience a stinging sensation or have some mild rhinitis.

### Licensed QIV

Occasionally, recipients of unadjuvanted licensed, QIVs may develop influenza-like reactions, such as fever, feverishness (chills/shivering/sweating), fatigue (tiredness), malaise (general unwell feeling), myalgia (body aches/muscular pain), arthralgia (joint pain), headache, and/or nausea. Some subjects may develop reactions at the injection site, including pruritus (itching), ecchymosis (bruising), erythema (redness), induration (hardness)/swelling, pain, and/or tenderness. Most of these reactions peak in intensity in the first 24 hours after vaccination and disappear without treatment within 1 or 2 days. Analgesics (e.g., acetaminophen, or ibuprofen or similar non-steroidal anti-inflammatory drugs (NSAIDs) and rest may generally relieve or lessen these reactions. Bruising can sometimes occur due to the vaccination procedure.

In addition, post-marketing surveillance indicates AESIs (autoimmune, auto-inflammatory and immune-mediated diseases) as potential risks identified for the seasonal influenza vaccines including, but not limited to, neuritis, convulsions, severe allergic reactions, syncope, encephalitis, thrombocytopenia, vasculitis, and Guillain-Barré syndrome. Reports of these reactions were rare; however, exact incidence rates cannot be precisely calculated.

### Allergic Reaction

Acute and potentially life-threatening allergic reactions are also possible. Very rarely, occurring in about 1 in 4 million people given a vaccination, there can be a serious allergic reaction to a vaccine. These reactions can manifest as skin rash (hives), swelling around the mouth, throat or eyes (angioedema), difficulty breathing (bronchospasm), a fast pulse (tachycardia), or loss of blood pressure (hypotension). If these reactions occur, they can usually be stopped by the administration of emergency medications by the study personnel. As with any vaccine or medication, there is a very small chance of a fatal reaction (death), although researchers do not expect this to occur.

### Blood Draw

Drawing blood may cause transient discomfort and fainting. Fainting is usually transient and managed by having the subject lie down and elevate his/her legs. Bruising at the blood draw site may occur, but can be prevented or lessened by applying pressure to the blood draw site for a few minutes after the blood is taken.

### Intramuscular Injection

Intramuscular injection may also cause transient discomfort and fainting. Giving an IM injection may also cause infection. The use of aseptic (sterile) technique will make infection at the site where blood will be drawn or where the study vaccination will be given extremely unlikely.

### Nasal Swabs

Obtaining a nasal swab may cause mild discomfort and on rare occasions may cause a nosebleed.

### Pregnancy

It is unknown if this vaccine poses any risks to an unborn child. As such, female adolescents of childbearing potential, i.e., women who have started menses, must agree to use an effective method of birth control for at least 30 days prior to first study vaccination and for at least 30 days following the second vaccination. Males who are sexually active with a female of childbearing potential must agree not to father a child for 30 days after receipt of the first study vaccination.

### Other Risks

In addition, post-marketing surveillance of seasonal influenza vaccines identified other adverse events including, but not limited to, neuritis, convulsions, severe allergic reactions, syncope, encephalitis, thrombocytopenia, vasculitis, and Guillain-Barré syndrome. Reports of these reactions were rare; however, exact incidence rates cannot be precisely calculated.

During the swine influenza (H1N1) vaccine campaign of 1976, some recipients developed a paralytic illness called Guillain-Barré syndrome (GBS). GBS is an acute inflammatory neuropathy characterized by weakness, hyporeflexia or areflexia, and elevated protein concentrations in cerebrospinal fluid. The rate of GBS was significantly increased in individuals receiving the 1976 swine influenza (H1N1) vaccine at about 1 per 100,000 vaccine recipients. This syndrome has not been seen consistently with other influenza vaccines. Most persons who develop GBS recover completely, although the recovery period may be as little as a few weeks or as long as a few years. About 30% of those with GBS still have residual weakness after 3 years and about 3% may suffer a relapse of muscle weakness and tingling sensations many years after the initial attack. Intensive surveillance of GBS after administration of inactivated influenza vaccines since 1976 has shown a slight increase in risk over background cases (more

than one additional case of GBS per million persons) following vaccination, typically with onset within 6 weeks after vaccination. Interestingly, although vaccination rates have increased in the last 10 years the numbers of reported cases of vaccine-associated GBS have declined. A recent study in Canada showed that the 2009 H1N1 vaccine was associated with a small but significant risk of GBS in persons 50 years and older. An active, population-based surveillance study conducted in the United States during the 2009-2010 influenza season found less than 1 excess GBS case per million doses of 2009 H1N1 vaccine administered – a rate similar to that associated with some previously administered annual influenza vaccines. Another study using the Medicare system showed an elevated risk of GBS with 2009 monovalent H1N1 vaccination (incidence rate ratio = 2.41, 95% confidence interval: 1.14, 5.11; attributable risk = 2.84 per million doses administered, 95% confidence interval: 0.21, 5.48). An international collaboration study also supported a conclusion of an association between 2009 H1N1 vaccination and GBS. It is unknown if the administration of the H3N2 M2SR and seasonal vaccines to be used in this study will result in the incidence of GBS as high as that seen with the 1976 vaccine product as the mechanism leading to this response has not been completely elucidated.

